### 12.10 Appendix 10. Medications That May Cause QTc Prolongation

A list of medications known to cause QTc interval prolongation is available at the following link: <https://crediblemeds.org/index.php/login/dlcheck>

If a participant in this study does not have access to the internet, they can contact the institution investigational pharmacy or contact their study physician to obtain a list.

Table 12-3 presents a list of drugs that may prolong QTc. This is not an inclusive list of drugs and is provided for guidance only. The participant is encouraged to follow the list in this link above for the most up-to-date information. These drugs are prohibited during the study. Washout period is based on roughly 5 half-lives and rounded to a convenient interval. This list includes (but is not limited to) the following:

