e ECGs and vital signs should be performed approximately 15 min prior to any invasive procedures including IV bag change, if applicable, and approximately 15 min prior to EOI. ECGs are only required in cycle 1 and 2.

f Cycle 2 day 1: vital signs measurement also required 1, 2, and 4 hours after infusion start.

g Cycle 3 and 4 day 1: vital signs measurement also required 1 and 2 hours after infusion start.

h As indicated in [Section 12.2](#), hematology and chemistry panels include differential cell counts and comprehensive metabolic profile, as well as serum uric acid and phosphorous levels, and liver function tests. Coagulation panel includes prothrombin time (PT), partial thromboplastin time (PTT), fibrinogen, and D-dimer.

i If ferritin value after CRS is abnormal, continue monitoring until values are back to baseline/event is resolved.

k PK sampling should be done approximately 15 min prior to EOI.

l Serum and urine immunofixation (IFE) for M-protein measurements. Urine IFE to be only followed up if positive for M-protein at baseline.

n Plasmacytoma assessments are to be repeated during treatment only to confirm a PR or better only if measurable plasmacytoma are present at baseline, to confirm PD, at initiation of other anti-MM treatment, or if clinically indicated. The same technique (may include MRI, PET-CT, or other standard-of-care method) must be employed for each measurement. Skeletal survey is not required for confirmation of PR or better.

o MRD and [REDACTED]

t See [Section 7.1.4](#) for details on premedication requirements.

**During the Long-term follow-up phase serious adverse events suspected to be related to investigational product that the investigator becomes aware of will be reported to Amgen.**

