### **Prior/Concomitant Therapy**

214 Previously received an allogeneic stem cell transplant and the occurrence of 1 or more of the following:

- received the transplant within 6 months prior to study day 1
- received immunosuppressive therapy within the last 3 months prior to study day 1
- any active acute graft versus host disease (GvHD), grade 2 to 4, according to the Glucksberg criteria or active chronic GvHD requiring systemic treatment
- any systemic therapy against GvHD within 2 weeks prior to start of investigational product treatment

215 Autologous stem cell transplantation < 90 days prior to study day 1

216 Treatment with systemic immune modulators including, but not limited to, nontopical systemic corticosteroids (unless the dose is  $\leq$  10 mg/day prednisone or equivalent), cyclosporine, and tacrolimus within 2 weeks before study day 1

217 Last anticancer treatment (chemotherapy, IMiD, PI, molecular targeted therapy) < 2 weeks prior to study day 1

218 Last treatment with a therapeutic antibody less than 4 weeks prior to study day 1

219 Radiation therapy to multiple anatomic sites within 28 days prior to study day 1. Focal radiotherapy within 14 days prior to study day 1.

220 Major surgery defined as surgery requiring general anesthesia with endotracheal intubation within 28 days prior to study day 1, unless discussed with and eligibility approved by Amgen medical monitor

221 Prior treatment with any drug that specifically targets BCMA on tumor cells (eg, other bi-specific antibody constructs, antibody drug conjugates, or CAR T-cells, except for subjects who were previously treated with AMG 420 in this study.

222 Treatment with medications known to cause QTc interval prolongation within the washout periods described in [Section 12.10](#) unless approved by the Amgen medical monitor

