#### 7.1.7 Excluded Treatments, Medical Devices, and/or Procedures During Study Period

The following treatments and/or procedures are excluded during the treatment period of the study (until SFU):

- any antitumor therapy other than AMG 420, such as:
  - cytotoxic and/or cytostatic drugs
  - radiation therapy (with the exception of radiotherapy for palliative care such as bone pain; this is only permitted after discussion with Amgen medical monitor)
  - immunotherapy

- any other immunosuppressive therapies (except for the management of acute, treatment-related toxicities such as transient - ie, for up to 2 weeks - use of corticosteroids and tocilizumab)
  - high-dose corticosteroid therapy (dexamethasone > 24 mg/day or equivalent) is only allowed for up to 7 days
- any other investigational agent
- treatment with medications known to cause QTc interval prolongation unless approved by the Amgen medical team (see [Section 12.10](#))
- any major surgery, except for surgery for palliative repair of pathologic fractures, as long as determined not to be due to disease progression
- none of the medications mentioned in [Section 7.8.2](#) are excluded during the study

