### **7.8.2 Concomitant Treatment**

Throughout the study, investigators may prescribe any concomitant medications or treatments deemed necessary to provide adequate supportive care except for those listed in [Section 7.1.7](#).

Concomitant therapies are to be collected from start of screening through the end of safety follow-up period.

All concomitant medications, including all prescription, over-the-counter, herbal supplements, and IV medications and fluids will be recorded on the eCRF.

During the LTFU period until EOS, any anti-multiple myeloma treatment is to be recorded.

For all concomitant medication collect therapy name, indication, dose, unit, frequency, route, start date, and stop date.

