#### 7.8.2.6 Infections

Prophylactic antibiotics, antifungal, and antivirals are allowed and should be given according to institutional standards. Pneumocystis prophylaxis should also be given according to institutional standards. For subjects who are considered to have an increased risk for herpes infections, prophylaxis is mandatory unless medically contraindicated. Subjects who may experience neutropenia for 7 days or longer are at a high risk for infectious complications. As appropriate, these subjects should be administered prophylactic antibacterial, antifungal, and antiviral medications. These subjects should be monitored for early signs of breakthrough infections after the initiation of antibacterial therapy to prompt additional evaluation and possible therapy modification.

Subjects presenting with evidence of active infection after the start of AMG 420 treatment should be closely monitored while being treated with AMG 420. Subjects with identified, active systemic infections requiring IV antibiotics, antivirals, or antifungals should not be dosed with AMG 420 until infection has resolved, and if being treated with an anti-infectious therapy, the course of such therapy should have been completed.

Patients who develop fever greater than 38.0°C lasting more than 1 hour or fever greater than 38.3°C of any duration during AMG 420 treatment should be promptly evaluated for infection as well as cytokine release syndrome (CRS). Workup should include evaluation for bacterial, fungal, and viral etiologies using radiographic imaging and appropriate microbiological/serologic assays, and empiric therapy should be considered using investigator's institutional standard of care approach. Guidelines for dose interruption and AMG 420 discontinuation as detailed in [Tables 7-1](#) and [7-2](#) should be followed. Investigators should consider the potential immunosuppressive effects of CRS rescue medications (eg, tocilizumab, corticosteroids) in their empiric management of fever. If patients develop febrile neutropenia (defined as ANC < 1000 10^6/L with a single temperature of > 38.3°C [101°F] or a sustained temperature of ≥ 38°C [100.4°F] for more than one hour), use of standardized guidelines for management and initial treatment of neutropenic fever (eg, Infectious Diseases Society of America Clinical Practice Guidelines, Management of Febrile Neutropaenia: ESMO Clinical Practice Guidelines) is encouraged.

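### Protocol 12.10 bans QT-prolonging drugs outright while 7.1.7 and criterion 222 allow them with approval, the rule for listed anti-infectives is unclear, and SAP 9.6.6 omits the QTcF change categories

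*Protocol*

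**What the plan says.** On the drugs:

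- Protocol 12.10 introduces its list of QT-prolonging medications and states "These drugs are prohibited during the study". It names no approval route. It also says that the list, Table 12-3, is guidance and not exhaustive.
- Protocol 7.1.7, which applies until the safety follow-up visit, excludes "treatment with medications known to cause QTc interval prolongation unless approved by the Amgen medical team" and refers to 12.10.
- Exclusion criterion 222 requires washout before entry, again with an exception: "unless approved by the Amgen medical monitor".
- The last bullet of 7.1.7 reads "none of the medications mentioned in [Section 7.8.2](#) are excluded during the study".
- The lead-in of 7.8.2 allows supportive medication, but not what 7.1.7 lists.
- Section 7.8.2.6 states "Prophylactic antibiotics, antifungal, and antivirals are allowed and should be given according to institutional standards" and "Pneumocystis prophylaxis should also be given according to institutional standards". It also holds AMG 420 in subjects with an active systemic infection that needs intravenous anti-infectives, until the infection has resolved and the course is complete.

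On ECGs, a footnote to Table 2-2 says "ECGs are only required in cycle 1 and 2", although the ECG row carries later marks that read as end of treatment and safety follow-up. Protocol 10.4.2.3.1 commits to summaries over time, to categories of each subject's largest QTcF change from baseline, and to categories of the largest post-baseline value. SAP 9.6.6 keeps the first and third. SAP section 10 says that nothing has changed from the protocol.

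**The concern.** A site that wants to give a listed drug needs one answer. The protocol can be read as forbidding it, as allowing it after approval, or, for an anti-infective, as leaving it outside the exclusions. Approval is the protocol's QT check before such a drug is given on study. The question is practical because anti-infective prophylaxis is expected in this population and Table 12-3 contains common members of those classes. Approval carries more weight after cycle 2, when routine ECGs are no longer required.

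On the analysis side, change in ECGs is among the primary safety endpoints in protocol 4.1. If the SAP is followed as written, the report will lack a summary that the protocol promises, and section 10 will tell the reader that nothing was dropped.

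**Working it through.** No sample-size or error-rate figure bears on this point. The check compares the texts and makes two small counts.

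**1. The rules side by side**

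| Place | Rule | Approver | Period |
|---|---|---|---|
| 12.10 | prohibited | none | the study |
| 7.1.7, QT bullet | excluded unless approved | sponsor's medical team | to safety follow-up |
| Criterion 222 | washout unless approved | sponsor's medical monitor | before entry |
| 7.1.7, last bullet | not excluded if mentioned in 7.8.2 | none | the study |
| 7.8.2 lead-in | allowed unless listed in 7.1.7 | not stated | the study |

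The first row contradicts the second for every listed drug. It also runs longer, because read literally the study includes long-term follow-up.

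**2. Overlap between Table 12-3 and 7.8.2.6**

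- Antibacterials: azithromycin, clarithromycin, erythromycin, gatifloxacin, gemifloxacin, grepafloxacin, levofloxacin, moxifloxacin, ofloxacin, sparfloxacin and telithromycin (11 entries).
- Antifungal: voriconazole (1). Antiviral: foscarnet (1). Used against Pneumocystis: pentamidine (1).
- Total 11 + 1 + 1 + 1 = 14 entries. Antimalarials and amantadine are not counted.

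This count shows that the sections overlap. It does not measure use.

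**3. Tracing one case, levofloxacin prophylaxis**

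- Section 7.8.2.6 allows antibiotics as a class.
- The lead-in of 7.8.2 excepts what 7.1.7 lists.
- The QT bullet of 7.1.7 requires approval.
- The last bullet of 7.1.7 says that medications in 7.8.2 are not excluded, which returns to the start.
- Section 12.10 forbids the drug even with approval.

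Neither 7.1.7 nor 7.8.2 says which takes precedence. A drug of the same class that does not prolong QT satisfies every section.

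**4. Which uses remain open**

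The hold in 7.8.2.6 removes concurrent exposure during intravenous treatment of active systemic infection. A restart after an adverse-event interruption repeats the assessments of cycle 1 days 1 to 3, which include ECGs. That leaves prophylaxis and oral or non-systemic treatment, which trigger no such hold.

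**5. ECG summaries**

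| Summary | Protocol 10.4.2.3.1 | SAP 9.6.6 |
|---|---|---|
| Values or changes over time | yes | yes |
| Maximum QTcF change, categorised | yes | no |
| Maximum post-baseline value, categorised | yes | yes |

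One of the two categorised summaries is missing. Summaries over time do not replace it, because they do not show how many subjects had a largest increase above a given limit. The SAP's definitions section already gives the QTcF formula, the averaging of triplicates and the change from baseline.

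**6. Could a version gap explain the omission?**

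The SAP was written to Amendment 4, and the current protocol is Amendment 5. The Amendment 5 rationale does not name 10.4.2.3.1 among the sections changed, so this is unlikely. It cannot be ruled out, because the text of Amendment 4 is not available and the rationale also mentions editorial changes throughout.

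**The case against.** The strongest reply on the drug rules is that no unsafe path follows from the first conflict. A site that follows 12.10 withholds the drug, and a site that follows 7.1.7 asks for approval. Section 7.1.7 is the operative rule, and approval is evidently what is intended. That stands, and it keeps the point minor. The two sections still tell sites different things.

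A reader might infer that the last bullet of 7.1.7 lets a listed anti-infective be given with no sponsor review. The documents do not support so firm a reading. Section 7.8.2 names classes and none of the 14 drugs counted above. Its lead-in defers to 7.1.7, and 7.1.7 has a specific QT bullet. The text is circular, which makes it unclear but does not make it a permission.

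A reader might also measure the problem by the share of treatment time after cycle 2. That share describes the ECG schedule and would be the same if the drug rules were perfectly worded. The documents also report no ECG effect of AMG 420 in the 28-day toxicology study, and entry requires a baseline QTcF of no more than 470 msec.

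On the SAP, it is fair to say that changes over time are kept and only one table is lost. A reader might add that 9.6.6 does not mention the protocol's listing of all ECG data. That is weak evidence, because SAP 9.6.3 and 9.6.4 do not restate the laboratory and vital-sign listings either. The missing category table is different: 9.6.6 restates its companion and leaves it out.

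**Conclusion.** The point holds and is minor. Protocol 12.10 contradicts 7.1.7 and criterion 222 on whether approval can permit a QT-prolonging drug. The circular references between 7.1.7 and 7.8.2 leave it unclear whether listed anti-infectives need approval, mainly for prophylactic, oral or non-systemic use. SAP 9.6.6 omits one of two categorised ECG summaries that the protocol plans for a primary safety endpoint, so the statement in SAP section 10 is inaccurate.

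No harm or event rate is claimed. The number of subjects taking a listed drug is not in the documents. The ECG tables are descriptive, and the enrollment-holding rules rest on DLT counts. The conclusion on the SAP assumes that Amendment 4 contained the same ECG text as the current protocol. If it did not, the SAP still differs from the protocol now in force.

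**What to change.** 1. In protocol 12.10, make the prohibition conditional on approval by the sponsor's medical team and cite 7.1.7, which also aligns the period.
2. In the last bullet of 7.1.7, state that the exemption for 7.8.2 medications is subject to the rule on QT-prolonging drugs.
3. In SAP 9.6.6, restore the categories of maximum QTcF change from baseline and state the category limits, which neither document gives. At minimum, record the removal in SAP section 10.

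The cost is one clause in each of two protocol sections and one descriptive table from data already collected. No sample size, visit or holding rule changes. The Amendment 5 rationale reports that the program has ended and that supply will not continue, so the protocol wording helps only subjects still on treatment. The SAP correction applies to the remaining analyses in any case.

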**Table 12-3. Medications That May Cause QTc Prolongation**

Compounds	Compound Half-Life	Possible Washout Period - Hours	Possible Washout Period - Days
Alfuzosin	~ 10 hours		7
Amantadine	17 ± 4 hours (10-25)		4
Amiodarone (cordarone)	58 days (15-142) 36 days (active metabolite)		180
Amitriptyline*	> 24 hours, wide interpatient variability		
Arsenic trioxide	not characterized		
Azithromycin	40 hours		
Bepidil	42 hours (26-64)		10
Chloral hydrate	readily converted to trichloroethanol (active metabolite T 1/2 = 7-10 hours)	48	
Chloroquine	prolonged (days to weeks)		
Chlorpromazine	30 ± 7 hours		
Clarithromycin	non-linear PK 3-4 hours (250 mg Q12) 5-7 hours (500 mg Q12)	36	
Chloroquine	6-60 days; mean 20 days		
Desipramine*	> 24 hours, wide interpatient variability		
Disopyramide	6.7 hours (4-10)	36	
Dofetilide	10 hours	48	
Dolasetron	8.1 hours		
Domperidone	7-8 hours	48	
Doxepin*	> 24 hours, wide interpatient variability		
Droperidol	2.2 hours	10	

Footnotes defined on last page of this table

**Table 12-3. Medications That May Cause QTc Prolongation**

Compounds	Compound Half-Life	Possible Washout Period – Hours	Possible Washout Period - Days
Erythromycin	*each salt form has different half-life*		
Felbamate	20-23 hours		5
Flecainide	20 hours (12-27)		5
Foscarnet	87.5 ± 41.8 hours *distribution and release from bone*		20
Fosphenytoin	12-29 hours		6
Gatifloxacin	7-14 hours	48	
Gemifloxacin	7 hours	48	
Grepafloxacin	16 hours		3
Halofantrine	6-10 days (variable among individual)		45
Haloperidol	18 ± 5 hours		5
Ibutilide	6 hours (2-12) *variable among subject*	36	
Imipramine*	> 24 hours, wide interpatient variability		
Indapamide	14 hours (biphasic elimination)		3
Isradipine	8 hours (multiple metabolites)	48	
Levofloxacin	6-8 hours	48	
Levomethadyl	multiple compartment PK with active metabolite 2.6 days for LAAM, 2 days for nor-LAAM, 4 days for dinor-LAAM		20
Lithium	24 hours (10-50)		7
Mesoridazine	24-48 hours (animal study)		10
Methadone	15-30 hours		7
Moexipril/HCTZ	2-9 hours (include active metabolite) for moexipril; 5.6-14.8 hours for HCTZ	48	
Moxifloxacin	12 ± 1.3 hours	72	
Naratriptan	6 hours	36	
Nicardipine	~ 2 hours post IV infusion	12	
Nortriptyline*	> 24 hours, wide interpatient variability		
Octreotide	1.7 hours	12	
Ofloxacin	5-7.5 hours		2
Ondansetron	4 hours (IV/IM); 3 hours (PO)		1 to 3
Pentamidine	6.4 ± 1.3 hours	36	
Pimozide	55 hours		10

Footnotes defined on last page of this table

**Table 12-3. Medications That May Cause QTc Prolongation**

Compounds	Compound Half-Life	Possible Washout Period – Hours	Possible Washout Period - Days
Procainamide	3-4 hours for PA and NAPA (active metabolite)	24	
Protriptyline*	> 24 hours, wide interpatient variability		
Quetiapine	6 hours	36	
Quinidine	6-8 hours in adult; 3-4 hours in children	36	
Quinine	4-5 hours		
Risperidone	3-20 hours (extensive to poor metabolizer) 9-hydroxyrisperidone (active metabolite) T ½ = 21-30 hours (extensive to poor metabolizer)		4
Salmeterol	5.5 hours (only 1 datum)	36	
Sotalol	12 hours	72	
Sparfloxacin	20 hours (16-30)		4
Sumatriptan	2.5 hours	12	
Tacrolimus	~ 34 hours in healthy; ~ 19 hours in kidney transplant		7
Tamoxifen	5-7 days (biphasic)		30
Telithromycin	2-3 hours	24	
Thioridazine	20-40 hours (phenothiazines)		7
Tizanidine	2.5 hours	12	
Vardenafil	4-5 hours		
Venlafaxine	5 ± 2 hours for parent comp. 11 ± 2 hours for OVD (active metabolite)	60	
Voriconazole	6 hours; dose dependent		
Ziprasidone	7 hours	36	
Zolmitriptan	2.8-3.7 hours (higher in female)	18	

Page 3 of 3

\* Weakly associated with Torsades de pointes and/or QT prolongation, but that are unlikely to be a risk for Torsades de pointes when used in usual recommended dosages and in patients without other risk factors (eg, concomitant QT prolonged drugs, bradycardia, electrolyte disturbances, congenital long QT syndrome, concomitant drugs that inhibit metabolism).

Sources: [Drug Facts and Comparison 2006, 2005](#); [Physician's Desk Reference, 2002](#); [Goodman & Gilman's the Pharmacological Basis of Therapeutics, 1996](#).

12.11 Appendix 11. Schedule of Activities in Case of Requirement for Dose Step

Table 12-4. Phase 1b Screening and Treatment Cycle 1 With Dose Step

	SCR	Treatment Period																										Infusion-free Interval a					
Cycle		1																															
Cycle Day	- 21 to -1	1						2	3	4						5	6	8	15	22	29	36											
Hours	Pre-dose	Relative to start of infusion												Pre-step	Relative to start of infusion												EOI						
		0	1	2	4	6	8	12	16	20	24	48	0.5		1	2	4	6	8	12	16	20	24	48									
GENERAL AND SAFETY ASSESSMENTS																																	
Informed consent	X																																
In-/Exclusion criteria	X																																
Demographics/Medical history	X																																
Hospitalization b		6 days																															
Concomitant medications		<----- continually from informed consent until SFU ----->																															
SAE review		<----- continually from informed consent until SFU ----->																															
AE review		<----- continually from first dose of AMG 420 until SFU ----->																															
Physical examination	X	X											X	X	X												X	X	X	X	X	X	X
Peripheral neuropathy	X																																
ECOG performance status	X	X																													X		
Height	X																																
Weight	X	X																															
Vital signs, pulse oximetry c	X	X		X	X	X	X	X	X	X	X	X	X	X	X		X	X	X	X	X	X	X	X	X	X	X	X	X	X	X	X	
ECG triplicate measurement c	X	X										X	X	X													X	X				X	

Footnotes defined after last page of table.

**Table 12-4. Phase 1b Screening and Treatment Cycle 1 With Dose Step**

	SCR	Treatment Period																												Infusion-free Interval a			
Cycle		1																															
Cycle Day	-21 to -1	1						2	3	4						5	6	8	15	22	29	36											
Hours	Pre-dose	Relative to start of infusion												Pre-step	Relative to start of infusion												EOI						
		0	1	2	4	6	8	12	16	20	24	48	0.5		1	2	4	6	8	12	16	20	24	48									
LABORATORY ASSESSMENTS																																	
Pregnancy test d	X	X																															
Coagulation e	X	X					X					X	X	X					X						X	X	X	X	X	X	X	X	
Hematology, chemistry e	X	X					X					X	X	X					X						X	X	X	X	X	X	X	X	
Creatinine Clearance	X																																
Ferritin f		X	←----- continue monitoring in case of CRS only -----→																														
Hepatitis serology	X																																
Latent TB test	X																																
Urinalysis	X	X											X	X													X	X	X	X	X	X	X
Ig: IgA, IgM, IgG	X	X																															
		█																															
PK ASSESSMENTS																																	
AMG 420 PK collection g		X										X	X	X													X	X	X	X	X	X g	

Footnotes defined after last page of table.

